4. SELECTION AND ENROLLMENT OF PARTICIPANTS

4.1 Inclusion Criteria

Participants must meet all of the following inclusion criteria to participate in this study:

- ≥ 13 years old
- Own a smartphone and are willing to receive information through it
- Received a liver or kidney transplant at a participating study site during or prior to the study period.

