4.3 Study Enrollment Procedures

Participants will be approached by the following methods:

For subjects ages 13-21 years old: either while they are an inpatient post-transplant or at any follow-up outpatient clinic visit by a study member to participate in this study.

For subjects >21 years old: either while they are an inpatient post-transplant or at their first post-op outpatient clinic visit by a study team member to participate in this study.

For all subjects:

When feasible to conduct in-person consenting, written consent will be obtained explaining the purpose of the study, their part in it, and that they can withdraw from the study at any time. As much time as necessary will be allowed for obtaining consent. Assent will be obtained from participants age 13-17 years, along with parental consent.

Additionally, we will make provisions for phone consent and enrollment if needed due to potential COVID-19 restrictions so that enrollment may proceed according to plan. If unable to conduct in-person consenting and enrollment process, patients will be contacted by phone and the study team will conduct the appropriate oral consent/assent procedures and conduct the procedures listed below remotely.

We will use block randomization to assign participants to the intervention or the control group using random block sizes ranging from 2 to 8. Block randomization will improve the probability of balanced groups over the course of the study as well as during shorter time horizons. A research data analyst, blind to the group allocations, will generate a list of sequential group assignments using this method. The list will be used to create sequentially numbered, sealed envelopes that will be used to allocate consenting participants to the control or intervention arms of our study. Each patient will have a 50% chance to be in the intervention arm of the study.

Participant enrollment will continue until we have reached 25 participants in each arm by age (13-21 years and 22 years and older) for a total of 100 participants and we will follow study participants for 12 months. No study visits are required of research participants after enrollment, but they will complete surveys and an interview over the phone.

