5.2.3 Follow-up Visits

After enrollment in the study, we will measure medication adherence in both arms at 3 month intervals for 12 months. MLVI, the standard deviation of recorded drug levels, will be calculated for each subject. Medication adherence will be ascertained through electronic health record (EHR) review of immunosuppression levels (i.e. tacrolimus, sirolimus, cyclosporine, prednisone, mycophenolate). Organ transplant recipients get labs post-transplant drawn frequently. Included in these lab draws are immunosuppression levels. A significant change in trough levels (i.e. undetectable or supra therapeutic) signal an issue of adherence to the prescribed regimen (i.e. missing doses, taking extra doses, etc.). We will track lab values using EHR, and record these in the secure REDCap database.

Participants in both arms will complete the immunosuppressant therapy instrument (ITAS), a validated tool to measure medication adherence at baseline for those subjects who have been on immunosuppressant therapy for at least 3 months at time of enrollment, at 12 weeks post enrollment for all subjects, and at 12 months post enrollment. Scores on the ITAS scale range from 0 (very poor adherence) to 12 (perfect adherence), and scores will be compared between the control and intervention arms (25). Participants will complete age appropriate QOLs at matching intervals to the ITAS. Follow-up questionnaires will be completed by phone with a designated study team member. Indicate treatment and followup visit assessments for each visit. List all measurements and procedures in bulleted format.

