9. STATISTICAL CONSIDERATIONS

Primary outcome variables:

12-week immunosuppression medication adherence:

We will measure medication adherence in both arms at 12 weeks. The Medication Level Variability Index (MLVI) will be used to analyze immunosuppression lab

values to determine adherence with a relative risk noted for standard deviation >2 .

Secondary outcome variables:

- Hospitalization days
- Biopsy-proven rejection
- Clinician-assigned rejection

We will recruit 100 liver and kidney transplant recipients (50/arm), and compare recipients who received the mHealth intervention to controls that did not receive it. The Medication Level Variability Index (MLVI) will be used to analyze immunosuppression lab values to determine adherence with a relative risk noted for standard deviation >2 . Descriptive statistics will be performed to compare frequencies of secondary outcomes (e.g., hospitalization, rejection, etc). Patient reported outcomes will be scored as appropriate and differences compared between treatment arms. Additionally, we will perform subgroup analyses for younger transplant recipients (age at transplant <40), older transplant recipients, men, and women.

In addition to understanding the efficacy of this technology in a transplant patient population, we will also evaluate the feasibility of implementing such a system into clinical workflow. We will examine time spent by reviewers each week using mDOT, most ideal time post-transplant to consent and educate participants on using the application, and streamlining the workflow involved in the application. In order to ensure acceptability among the patients who will be using the app, we will survey all participants in the intervention arm at the end of the study period on their overall satisfaction in using the app. This survey will be administered with the ITAS scale over the phone. In addition, we will also examine consent rate and use of the mDOT app by participants over time to understand acceptability of using the application.

Feasibility will also be measured through phone interviews with all study participants at 12 months. We will contact all patients who consented to be in the study to participate in the phone interviews. The interviews will be semi-structured, with a set of pre-written questions as the guide. All interviews will be audio recorded. Transcription of the interviews will be conducted by Production Transcripts, Inc.

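### The primary relative risk has no planned stratification by time on immunosuppression, although ages 13-21 mix new and established recipients; the loss is precision and protection against chance imbalance, not validity

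*Combined protocol and SAP*

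**What the plan says.** **Analysis.** Section 9 will "compare recipients who received the mHealth intervention to controls that did not receive it", using MLVI at 12 weeks "with a relative risk noted for standard deviation >2". It states no model, test, confidence interval, covariate or stratum for this comparison. The planned subgroups are age at transplant (split at 40) and sex.

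**Who enters, and when.** Section 4.1 admits anyone who "Received a liver or kidney transplant at a participating study site during or prior to the study period", with no upper limit on time since transplant. Section 4.3 then sets different approach windows by age:
- Ages 13-21: "either while they are an inpatient post-transplant or at any follow-up outpatient clinic visit by a study member".
- Over 21: "either while they are an inpatient post-transplant or at their first post-op outpatient clinic visit".

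**Balance.** Section 4.3 recruits to "25 participants in each arm by age (13-21 years and 22 years and older) for a total of 100 participants". Randomisation is in blocks of 2 to 8. Time since transplant is not mentioned as a randomisation factor.

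**What is known at baseline.** Section 5.2.3 gives the ITAS "at baseline for those subjects who have been on immunosuppressant therapy for at least 3 months at time of enrollment". Time on therapy therefore has to be known at enrolment, at least as under or over 3 months. The schedule in Section 5.1 lists baseline clinical, demographic and laboratory information but does not name this item.

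**The concern.** MLVI is the standard deviation of measured drug levels, so it reflects variation from any cause. It is reasonable to expect levels to vary more in the first weeks after transplant than in someone established for years, whatever the adherence. For a new recipient the 12-week window falls in that early period; for an established recipient it does not. The 13-21 group contains both kinds of participant by design.

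If time on therapy does predict MLVI above 2, leaving it out has two consequences. The standard error is larger than it needs to be. And with only 25 per arm aged 13-21, a chance excess of new recipients in one arm shifts the observed relative risk in a way that could be mistaken for an app effect or could mask one. A baseline value that the trial needs anyway would reduce both.

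**Working it through.** The plan gives no figure to reproduce here: the sample size comes without an event rate, effect size, alpha or power. The check asks how much stratifying would change.

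**Inputs from the documents.** 50 per arm (Section 9); 25 per arm in each age group, and the entry windows (Section 4.3).

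**Assumptions, not in the documents.** All adults are new. Either 20% or half of those aged 13-21 are new. P(MLVI >2) in new v established recipients is 50% v 30%, 60% v 30%, 70% v 20%, 70% v 30% or 80% v 20%.

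**1. Chance of imbalance in ages 13-21.** Let X and Y be the numbers of new recipients in the two arms, each binomial(25, p).
- p = 0.2: P(|X − Y| ≥ 5) = 0.110.
- p = 0.5: P(|X − Y| ≥ 5) = 0.203. If exactly 25 of the 50 are new, so that the total is fixed, the hypergeometric value is 0.258.

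**2. Effect of such an imbalance when the app does nothing.** Take half new, split 10 v 15. Expected events per arm = 25 adults × P(new) + new young × P(new) + established young × P(established).
- 70% v 30%: 17.5 + 10(0.7) + 15(0.3) = 29, against 17.5 + 15(0.7) + 10(0.3) = 31. RR = 29/31 = 0.935.
- 70% v 20%: 17.5 + 7 + 3 = 27.5, against 17.5 + 10.5 + 2 = 30. RR = 27.5/30 = 0.917.

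To put the first in proportion: the average event rate at 70% v 30% is 30/50 = 0.6, so the SD of the crude log RR is about √(2 × 0.4/(50 × 0.6)) = √0.0267 = 0.163. The shift is ln 0.935 = −0.067, about 0.4 of one standard error.

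**3. Variance of the log relative risk, crude v Mantel-Haenszel.** Simulation of the whole trial with no app effect, half of ages 13-21 new, stratified by new v established only:

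| P(MLVI >2), new v established | Change in variance |
|---|---|
| No association | loss of under 1% |
| 50% v 30% | about −2% |
| 60% v 30% | about −4% |
| 70% v 30% | about −9% |
| 80% v 20% | about −22% |

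At 70% v 30% the SD falls from 0.163 to about 0.163 × √0.91 = 0.156.

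**4. Power at a true relative risk of 0.6 (two-sided 5%, whole trial).** Crude v stratified: 47.1% to 47.7% (50% v 30%), 58.4% to 58.8% (60% v 30%), 70.2% to 71.5% (70% v 30%), 77.5% to 82.7% (80% v 20%).

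**5. Error rate of the unadjusted test.** In the same simulations it rejected in 3.8% to 5.5% of whole-trial null runs, so there is no material inflation.

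**The case against.** The strongest objection is that the size of the problem rests on an association the documents never quantify. No section relates time since transplant to MLVI. The only rates given, in Section 2, are non-adherence of 15-40% in adults and 50-70% in adolescents. Treating all adults as new with high MLVI rates reverses that order. Those figures are neither rates of MLVI above 2 nor split by time since transplant, so they do not refute the assumption, but they give it no support. At a moderate association the gain is about 2% in variance and about half a point of power. This stands, and it is why the size is given as a range that includes no gain.

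Three stronger readings are tempting, and the documents do not support them:
- **That the unadjusted relative risk is biased.** It is not. Allocation is randomised, and chance imbalance is already covered by the test's error rate.
- **That the plan has chosen a crude analysis.** Section 9 is silent on method. The absence of adjustment is read from that silence.
- **That time since transplant is already recorded.** The ITAS rule implies that time on therapy is checked at enrolment, and the age-at-transplant subgroups point the same way, but neither is listed as a data item. Time on therapy is also a proxy for time since transplant, not the same variable.

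Finally, a two-level split cannot remove all imbalance: it groups a recipient at 4 months with one at 10 years. Because adults are nearly all new, the split is also entangled with age group, so age belongs in the analysis too.

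**Conclusion.** The point holds as a recommended improvement to an under-specified primary analysis. The 13-21 group mixes new and established recipients by design, and neither the stated randomisation nor Section 9 takes account of it. The benefit of stratifying is small if the association is moderate (about 2% of the variance at 50% v 30%) and material only if it is strong (about 22% at 80% v 20%). An imbalance of 5 or more new recipients among ages 13-21 would arise in roughly 1 trial in 9 to 1 in 5; with half new and rates of 70% v 20-30%, a difference of 5 moves a null relative risk to 0.92-0.94. All of these sizes depend on the assumed rates, the assumed share of new recipients, and all adults being new. The case for acting is that the protection is nearly free and is credible only if fixed before the data are seen.

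**What to change.** In Section 9, pre-specify the primary relative risk as stratified (Mantel-Haenszel) by, or adjusted (modified Poisson model with robust standard errors) for:
- time on immunosuppression at enrolment, under 3 months v 3 months or more, the split that the ITAS rule in Section 5.2.3 already needs; and
- enrolment age group, 13-21 v 22 and older, by which recruitment is already balanced.

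Report the crude relative risk as supportive. Name time on immunosuppression as a baseline data item in Section 5.

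**Cost.** SAP wording and one named baseline field; no extra visits or participant burden. If the factors do not predict MLVI there is a slight loss of precision (under 1% of variance for the time split alone; the age term was not included in the calculations above). Some strata will be small, and adults at 3 months or more may be nearly absent, so the text should say how sparse or empty strata are handled.

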1.2 Secondary Objectives

- Clinical endpoints including rejection and hospitalization
- Patient reported adherence on immunosuppressant therapy instrument (ITAS)
- Patient-reported QoL outcomes as measured by PedsQL and SF-36
- Patient-reported self-efficacy using the Riekert Self-efficacy scale
- Patient-reported usability using the PSSUQ (treatment arm only)
- To examine the patterns of medication adherence in transplant recipients in both groups to better understand baseline medication adherence
- To understand the feasibility and acceptability of implementing such a system into the clinical workflow and patient follow-up care management

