5. STUDY PROCEDURES

5.1 Schedule of Evaluations

Procedure	Baseline	3 months	6 months	9 months	12 months
Informed Consent	X				
Randomization	X				
Baseline clinical/demographic/lab info/baseline survey	X				
Immunosuppression levels and laboratory values collected from medical record	X	X	X	X	X
Interval health information collected		X	X	X	X
Patient-reported outcomes*	X	X			X
Phone Interview					X

*these include ITAS, PedsQL <18 years at enrollment or SF-36 if >18 years at enrollment, Reikert self-efficacy scale, PSSUQ (treatment arm only and only at 3 months)

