We will use block randomization to assign participants to the intervention or the control group using random block sizes ranging from 2 to 8. Block randomization will improve the probability of balanced groups over the course of the study as well as during shorter time horizons. A research data analyst, blind to the group allocations, will generate a list of sequential group assignments using this method. The list will be used to create sequentially numbered, sealed envelopes that will be used to allocate consenting participants to the control or intervention arms of our study. Each patient will have a 50% chance to be in the intervention arm of the study.

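### Section 9 gives the baseline ITAS, quality-of-life and self-efficacy scores no use in the analysis; adjusting for them would add precision at no data cost

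*Combined protocol and SAP*

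**What the plan says.** Section 1.2 lists ITAS adherence, quality of life by PedsQL and SF-36, and "Patient-reported self-efficacy using the Riekert Self-efficacy scale" among the secondary objectives. The schedule in Section 5.1, like the one in the synopsis, marks patient-reported outcomes at baseline, 3 months and 12 months. Its footnote lists the instruments as "these include ITAS, PedsQL <18 years at enrollment or SF-36 if >18 years at enrollment, Reikert self-efficacy scale, PSSUQ (treatment arm only and only at", and closes by naming the 3-month visit for PSSUQ.

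Two sentences describe the analysis:

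- Section 9: "Patient reported outcomes will be scored as appropriate and differences compared between treatment arms".
- Section 5.2.3, on ITAS: "scores will be compared between the control and intervention arms".

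Neither names a model, covariate, time point or estimate, and no other section supplies one.

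Section 5.2.3 also limits who has a baseline ITAS. It is taken "at baseline for those subjects who have been on immunosuppressant therapy for at least 3 months at time of enrollment", and quality of life is to follow the ITAS timing. The schedules carry no such restriction. Section 4.3 approaches participants over 21 in hospital after transplant or at the first post-operative clinic visit, and those aged 13-21 in hospital or at any follow-up visit.

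**The concern.** The trial collects a pre-intervention score on the same scale as the outcome and then states no use for it. When a follow-up score correlates with its own baseline, chance baseline differences between arms carry into the follow-up comparison. With 50 per arm, and fewer within PedsQL or SF-36, these differences need not be small. Adjustment removes that part of the noise.

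What is at stake is the width of the confidence intervals for three secondary objectives. There is a second cost. With nothing prespecified, the analyst can choose among follow-up score, change score and adjusted score after seeing the data, and these differ in precision.

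**Working it through.** **Inputs from the documents**

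- Size: "25 participants in each arm by age (13-21 years and 22 years and older) for a total of 100 participants" (Section 4.3), so 50 per arm.
- Allocation: "Each patient will have a 50% chance to be in the intervention arm of the study" (Section 5.2.1).
- Instruments with both a baseline and a control arm: ITAS, PedsQL or SF-36, and self-efficacy. PSSUQ has neither.

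**Inputs assumed, because the documents give none**

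- Baseline-to-follow-up correlation r of 0.4, 0.5 or 0.6.
- Share f of participants with a baseline score: 1 or 0.5.
- For the power illustration only: difference of 0.5 SD, two-sided alpha 0.05, no dropout.

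The plan states no power or precision figure for these outcomes, so there is none to reproduce.

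**Why f = 0.5 is a plausible case for ITAS.** The 22-and-over group is 50 of the 100 participants. Section 4.3 recruits those over 21 around the time of transplant, so most will have been on therapy for less than 3 months and have no baseline ITAS. Some of the 13-21 group will also lack one, so the share could be below half.

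**Formulas (variance relative to comparing follow-up scores alone)**

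- ANCOVA, baseline in everyone: 1 - r². Equivalent gain in participants: 1/(1 - r²) - 1.
- ANCOVA with a missing-baseline indicator, share f with a baseline: residual variance is f(1 - r²) + (1 - f) = 1 - f·r². At f = 0.5 this is 1 - r²/2.
- Complete-case ANCOVA on that share: (1 - r²)/f. At f = 0.5 this is 2(1 - r²).
- Change score, baseline in everyone: 2(1 - r).

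| r | ANCOVA, all | Gain in participants | Missing indicator, half | Complete case, half | Change score, all |
|---|---|---|---|---|---|
| 0.4 | 0.84 | 19% | 0.92 | 1.68 | 1.2 |
| 0.5 | 0.75 | 33% | 0.875 | 1.50 | 1.0 |
| 0.6 | 0.64 | 56% | 0.82 | 1.28 | 0.8 |

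**Interval width.** Taking square roots, full-baseline ANCOVA gives intervals 0.92 / 0.87 / 0.80 times as wide as the unadjusted ones. The half-baseline missing-indicator analysis gives 0.96 / 0.94 / 0.91 times.

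**Illustrative power.** Unadjusted, 50 per arm: 70.5%. ANCOVA with a baseline in everyone: 77.9% / 82.3% / 87.8%. Complete-case ANCOVA on 25 per arm: 48.8% / 53.2% / 59.9%, below the unadjusted analysis each time. In variance terms, complete-case ANCOVA on half the sample loses whenever 2(1 - r²) > 1, that is, r below about 0.71.

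**Weaker correlation.** At r = 0.2 the cut is 0.2² = 4% with a baseline in everyone and 2% with a baseline in half.

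These are large-sample formulas. Estimating the slope costs a little precision. That is negligible with 100 participants but less so within PedsQL, whose numbers the documents do not give.

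**The case against.** The strongest reply is that the plan is silent rather than wrong. A reader might infer that it has chosen to ignore the baseline scores. The text does not support that: it names no model at all, and differences in Section 9 could even mean differences in change from baseline. This stands, so the finding is that no use of the baseline is stated, not that its use is excluded. The remedy does not change. Since 1 - r² = (1 - r)(1 + r), ANCOVA variance is below the change-score variance 2(1 - r) for every r below 1.

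A second reply is that the gain is smaller than the textbook figure, because many participants will have no baseline ITAS and perhaps no baseline quality of life. This also stands. The full-baseline figures are a best case, and Section 5.2.3 places no limit only on self-efficacy. It does not remove the gain. Time on therapy is fixed before allocation, so a missing-baseline indicator keeps everyone in without breaking the randomised comparison.

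A third reply is that only precision is at stake. That is correct. A reader might infer that the unadjusted comparison is biased or its intervals invalid; under randomisation neither follows. Section 9 also leaves patient-reported outcomes off its list of secondary outcome variables, and no power claim rests on them. This limits the importance of the point.

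**Conclusion.** The point holds as a free improvement. Three secondary objectives have scheduled baseline scores with no stated analytic use, and adjusting for those scores would sharpen the comparison without further data.

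With r of 0.4 / 0.5 / 0.6, variance falls by 16% / 25% / 36% if everyone has a baseline, and by about 8% / 12.5% / 18% if half do. The correlation and the half share are both assumptions, and weaker correlations or a lower share give less.

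A reader might extend the point to all four patient-reported objectives. PSSUQ must be left out, because it is collected only in the treatment arm and only at 3 months. A reader might also infer that any baseline adjustment helps. Complete-case ANCOVA would not if about half the baselines are absent and r is below about 0.71.

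**What to change.** In Section 9, replace the sentence on patient-reported outcomes with a prespecified analysis:

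- For ITAS, SF-36, PedsQL and self-efficacy, at 3 and at 12 months, fit an ANCOVA of the follow-up score on arm and the baseline score of the same instrument. Report the adjusted difference with a 95% CI.
- Add age group (13-21 / 22 and over) as a covariate, except for PedsQL. Everyone given PedsQL is under 18, so the term is constant there and cannot be estimated.
- Fit PedsQL and SF-36 separately.
- Where a baseline is absent by design (ITAS, and quality of life if it follows the ITAS timing), set the baseline to a constant and add a missing-baseline indicator, so that no one is dropped.
- Describe PSSUQ in the treatment arm only.

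Reconcile the schedules in the synopsis and Section 5.1 with the baseline restriction in Section 5.2.3, and say whether that restriction covers quality of life. State also that baseline scores are taken before allocation. Section 5.2.1 puts the baseline survey before randomisation but does not say that these instruments are part of it.

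The cost is SAP wording and a few lines of code. No extra data, visits or participants are needed.

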Participants will be enrolled in the study for 12 months. All subjects will complete study assessments and have immunosuppressant levels and clinical outcomes followed for 12 months. Subjects randomized to the intervention group will use the app for the first 3 months following enrollment. Subjects randomized to the control group will not use the app and will follow routine standard of care.

No study visits are required of research participants after enrollment, but they will complete surveys and an interview over the phone.

Procedure	Baseline	3 months	6 months	9 months	12 months
Baseline clinical/demographic/lab info/baseline survey	X				
Immunosuppression levels and laboratory values collected from medical record	X	X	X	X	X
Interval health information collected		X	X	X	X
Patient-reported outcomes*	X	X			X
Phone Interview					X

*these include ITAS, PedsQL <18 years at enrollment or SF-36 if >18 years at enrollment, Reikert self-efficacy scale, PSSUQ (treatment arm only and only at 3 months)

Sample Size and Population:

Participant enrollment will continue until we have reached 25 participants in each arm by age (13-21 years and 22 years and older) for a total of 100 participants. We will follow all study participants for 12 months.

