2. BACKGROUND AND RATIONALE

In adolescent and adult solid organ transplant recipients, poor adherence to immunosuppressant medications carries the risk of graft rejection, short- and long-term post-transplant complications, and increased healthcare costs (1-8). In transplant recipients, adherence to immunosuppressive drugs, as well as general medical indications is imperative to overall outcomes (9). The rate of non-adherence to immunosuppressive medications in transplant patients varies vastly, with reports ranging from 15-40% in adults and much higher at 50-70% among adolescents (9-14). Additionally, medication adherence is a key concern in the transition from adolescent to adult-centered transplant care, and transition planning should be prioritized in these transplant patients (15-18). Because of lacking objective and accurate non-adherence measurements, both to immunosuppressive drugs and medical indications, the true implications and prevalence of non-adherence is not yet well understood (19-21). Therefore, we believe that mobile health (mHealth) technology has the potential to allow clinicians and researchers to more comprehensively address and understand non-adherence in adolescent and adult transplant recipients.

emocha Mobile Health Inc. has developed an application that enables users to track dose-by-dose medication adherence through asynchronous, video directly observed therapy (DOT). This helps patients take their medication as prescribed and gives providers the assurance that their patients are supported and successful in treatment. DOT is the practice of watching a patient take every dose of medicine in-person, and has typically only been done in extreme cases because it can be both costly and burdensome: DOT is the standard of care for Tuberculosis treatment and has proven high-adherence rates. Through mHealth technology, DOT can be used more broadly and without added burden; emocha's technology allows this through enabling patients to use their mobile application

to view their regimen, record themselves taking every dose of their medication, report side effects or symptoms, visualize their treatment progress, and access educational content. This information is encrypted and transmitted to a HIPAA-secure web portal for providers to review. The aim of this study is to conduct a randomized control trial to compare medication adherence between patients who use the mHealth system against controls who do not.

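### Enrolment is filled by age group (13-21 and 22 or older), but the only planned age analysis cuts at age 40 at transplant, so neither enrolled group has a prespecified effect estimate

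*Combined protocol and SAP*

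**What the plan says.** **Enrolment.** The synopsis (Sample Size and Population) and section 4.3 both state: "Participant enrollment will continue until we have reached 25 participants in each arm by age (13-21 years and 22 years and older". The four cells together make 100.

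**Background.** Section 2 describes non-adherence as varying widely, with "reports ranging from 15-40% in adults and much higher at 50-70% among adolescents", and says that "medication adherence is a key concern in the transition from adolescent to adult-centered transplant care".

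**Analysis.** Section 9 gives 50 per arm and will "compare recipients who received the mHealth intervention to controls that did not receive it". The MLVI is to be used "to determine adherence with a relative risk noted for standard deviation >2". No age term or age stratum is named for this comparison. The subgroup sentence reads: "we will perform subgroup analyses for younger transplant recipients (age at transplant <40), older transplant recipients, men, and women". The only other use of age is the choice of quality-of-life instrument around age 18, which is not an effect analysis.

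**Recruitment windows (section 4.3).** These differ by age group: "For subjects ages 13-21 years old: either while they are an inpatient post-transplant or at any follow-up outpatient clinic visit", against "For subjects >21 years old: either while they are an inpatient post-transplant or at their first post-op outpatient clinic visit".

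**The concern.** Age group is the only participant characteristic for which the plan fixes numbers, and by the protocol's own background it is strongly related to the outcome. The analysis then sets it aside for a different cut on a different age (age at transplant). Three things follow.

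- A result for ages 13-21, or for all those aged 22 or older, could be produced only post hoc, which is weaker evidence.
- The under-40 result would mix participants aged 13-21 with an unplanned share of adults, and the older group would leave those adults out.
- A primary comparison that ignores a factor held fixed by quota and related to outcome reports a standard error somewhat larger than it need be.

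**Working it through.** **1. The plan's own figure.** 25 per arm × 2 arms × 2 age groups = 100, and 25 × 2 = 50 per arm. Both match section 9. The documents give no alpha, power or effect size, so there is no power calculation to reproduce.

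**2. Who is in the under-40 group.** All 50 participants aged 13-21 were transplanted before 40. Let q be the share of those aged 22 or older who were transplanted before 40. The documents do not give q, so a range is assumed. Group size = 50 + 50q.

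| q | Under 40 | Adults in it | 40 or older |
|---|---|---|---|
| 0 | 50 | 0% | 50 |
| 0.2 | 60 | 17% | 40 |
| 0.5 | 75 | 33% | 25 |
| 1 | 100 | 50% | 0 |

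The two splits coincide only at q = 0, which no eligibility criterion ensures.

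**3. Dilution.** Section 2's rates serve as stand-in control risks: pa = 0.50, 0.60 or 0.70 for ages 13-21 and pb = 0.15, 0.275 or 0.40 for 22 or older (0.60 and 0.275 are the midpoints). These are general non-adherence rates, not the risk of MLVI SD >2, and adolescent rates are applied to the whole 13-21 band. Suppose the app halves risk in ages 13-21 only, with q equal in both arms:

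RR under 40 = (pa/2 + q·pb) / (pa + q·pb)

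- q = 0.2: 0.52 (0.70/0.15) to 0.57 (0.50/0.40); midpoint rates 0.54.
- q = 0.5: 0.55 to 0.64; midpoint rates 0.59.

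**4. Precision of the 13-21 estimate in the same scenario.** SE of log RR = √[(1−pa)/(25pa) + (1−pa/2)/(25pa/2)]. At pa = 0.60 this is √(0.4/15 + 0.7/7.5) = 0.346. The 95% CI multiplies and divides the RR by exp(1.96 × 0.346) = 1.97, giving 0.25 to 0.99. The factor is 2.2 at pa = 0.50 and 1.8 at pa = 0.70.

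**5. Precision at 22 or older, no effect.** Factor = exp(1.96·√[2(1−pb)/(25pb)]): 2.0 at 0.40, 2.5 at 0.275 and 3.7 at 0.15. The last rests on 25 × 0.15 = 3.75 expected events per arm and is only approximate.

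**6. Ratio of the two RRs** (halving in ages 13-21, no effect in the others). SE² = (1−pa)/(25pa) + (1−pa/2)/(25pa/2) + 2(1−pb)/(25pb). The true difference is ln 2 on the log scale. The 95% CI factor is 2.5 to 4.6. Power at two-sided 0.05 (assumed) is 14-33%, and 23% at midpoint rates.

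**7. Primary comparison, crude versus stratified.** With 25 in each of the four cells and no effect, p̄ = (pa + pb)/2:

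- Crude variance of log RR = (1−p̄)/(25p̄)
- Mantel-Haenszel variance = [pa(1−pa) + pb(1−pb)] / [12.5(pa + pb)²]

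| pa/pb | Crude | Stratified | Variance ratio | Narrowing of log-scale CI (1 − √ratio) |
|---|---|---|---|---|
| 0.50/0.40 | 0.0489 | 0.0484 | 0.99 | 0.5% |
| 0.60/0.275 | 0.0514 | 0.0459 | 0.893 | 5.5% |
| 0.70/0.15 | 0.0541 | 0.0374 | 0.691 | 17% |

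With equal cells the two point estimates are identical, so their true sampling variance is the same. Only the reported SE, and hence the CI, changes.

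**The case against.** The strongest reply is that no objective asks for an effect by age and no text says why enrolment is split. A quota may serve only to secure representation, and section 9 does already name an age subgroup. This stands. A reader might infer that the quota was set up to support age-specific estimates which section 9 then dropped; the documents do not say so.

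A reader might also infer that the primary comparison is biased, or that stratifying makes the estimator itself more precise. Neither follows: with 25 per cell the crude and stratified estimates coincide, and the 17% figure needs the extreme pairing of 0.70 with 0.15.

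The dilution is also small. At midpoint rates it moves an RR of 0.50 by 0.04 to 0.09, well inside a CI of 0.25 to 0.99. The stand-in rates may overstate the age contrast, because those reported for adolescents are applied to 18-21-year-olds as well. A lower rate in that part of the band would shrink the gain from stratifying.

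Low power does not favour the 40 cut, however. If half of those aged 22 or older were transplanted before 40, the older group would have 25 people in total, fewer than the 50 in either enrolled age group. And whatever the quota's purpose, a group mixing ages 13-21 with an unknown share of adults is hard to interpret.

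**Conclusion.** The point holds as a misalignment between design and analysis. Neither enrolled age group has a prespecified effect estimate, and the 40 cut cannot stand in for one unless no enrolled adult was transplanted before 40. The primary comparison remains valid.

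The numerical cost is modest: a diluted RR of about 0.52-0.64 where 0.50 is true in ages 13-21, and a reported primary CI that stratification would narrow by about 0.5-17% on the log scale. The main loss is that any later statement about either age group would be post hoc.

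These sizes assume 20-50% of the older group transplanted before 40, section 2's rates as stand-ins for the MLVI risk, a halving confined to ages 13-21 for the dilution, no effect for the stratification comparison, and exactly 25 per cell. The absence of a prespecified estimate depends on none of these. The change is worth making because it is nearly free.

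**What to change.** In section 9:

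- Make 13-21 versus 22 or older, by age at enrolment, the prespecified age subgroup.
- Report the RR with 95% CI in each group, and the ratio of RRs with 95% CI, as descriptive estimates.
- Include age group as a stratum or covariate in the primary arm comparison.
- Keep the 40 cut as exploratory.
- State in one sentence why enrolment is split by age.

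The plan should also state the limits. CIs will be wide, interaction power low, and events sparse at 22 or older if the rate is low. A single stratified RR assumes a similar effect in both groups. Age group is partly confounded with time since transplant, because the recruitment windows differ. The block randomisation described names no age stratum, so that method does not by itself secure exactly 25 per arm in each age group.

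The cost is analysis-plan wording. Age at enrolment is already needed for the quota; no extra participants, visits or data are required.
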